### **7.7 Statistical Analysis**

The statistical analysis will be primarily descriptive in keeping with the exploratory nature of the study. All adverse events will be described and exact 95% confidence intervals will be produced for adverse event rates, both overall and within major categories. The change in the ratio of CART-19 cells over time will be compared using a Wilcoxon signed-rank test for paired data. This nonparametric test is very efficient (>95%) compared to the t-test if the underlying data are normally distributed. Analysis of other secondary endpoints such as anti-tumor activity will also be primarily descriptive and may include summary statistics such as means and standard deviations or Kaplan-Meier curves for survival information. Descriptive statistics may also be summarized for the exploratory endpoint.

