### **3 STUDY DESIGN**

#### **3.1 General Design**

We have designed a single-arm open-label phase I/IIa study to determine the safety, tolerability and engraftment potential of CART-19 T cells in patients with CD19+ hematologic malignancies. The general protocol schema is shown above in **figure 1** in section 1. All subjects will be dosed with CART-19 T cells. In all subjects treated to date, the CART-19 T cells contained only the TCR $\zeta$ :4-1BB transgene. A total of 72 subjects will be infused across “no allo”, “allo”, and CNS-3 cohorts. In order to infuse 72 patients, assuming a 20% drop out rate, we would enroll up to 86 patients.

A secondary objective is to determine if the 4-1BB transgene is superior to the TCR $\zeta$  only transgene. To test this, a cohort of 5 patients will be dosed with mixtures of TCR $\zeta$ :4-1BB and TCR $\zeta$  only cells, using a competitive repopulation strategy to determine the optimal signal transduction module in the chimeric receptor (**figure 13**). This cohort will proceed only after the 2 CARs to be compared are finalized. It is reasonable to assume that engineered T cells containing signaling domains that mimic physiologic signaling will function best in vivo, and therefore, we think that CART-19:TCR $\zeta$ :4-1BB will be superior to CART-19:TCR $\zeta$  only. **The null hypothesis is that they are equivalent.**

At entry, subjects will be staged and the suitability of their T cells for CART-19 manufacturing will be determined. Subjects in both the no allo and allo cohorts who have adequate T cells will be leukapheresed to obtain large numbers of peripheral blood mononuclear cells (PBMC) for CART-19 manufacturing. In each cohort, the subject is pheresed; however, in the allo cohort, T cells derived from donor engrafted cells may be collected from the subject. The T cells will be purified from the PBMC, transduced with CART-19 lentiviral vector, expanded in vitro and then frozen for future administration. Chemotherapy will then be given. Following tumor burden reassessment, CART-19 cells will be thawed and infused.

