Regardless of timing, toxicities that would preclude a subsequent dose of T cells are DLTs (defined in section 8.1) or GVHD attributable to the cell infusion, and not non-DLT toxicities or toxicities attributable to the prior chemotherapy, such as cytopenias. A DLT will prevent the infusion of the next dose, even if fully resolved by that time.

The cells are thawed by the [REDACTED]. The thawed cells will be given as a slow IV push or infusion rate as quickly as tolerated so that the duration of the infusion will be approximately 10-15 minutes, adjusted for size of patient and volume of infusion. In subjects 15-20 who receive mixtures of CART-19 cells, in order to facilitate mixing, the cells may be administered simultaneously using a Y-adaptor. Subjects will be infused and premedicated as described in section 5.3. Subjects' vital signs will be assessed and pulse oximetry will be done prior to dosing, at the end of the infusion and every 15 minutes thereafter for 1 hour and until these are stable and satisfactory. A blood sample for determination of baseline CART-19 level is obtained before infusion.

Patients experiencing toxicities from their preceding cytoreductive chemotherapy will have their infusion schedule delayed until these toxicities have resolved. The specific toxicities warranting delay of T cell infusions include: 1) Pulmonary: Requirement for supplemental oxygen to keep

CONFIDENTIAL

saturation greater than 95% or presence of radiographic abnormalities on chest x-ray that are progressive; 2) Cardiac: New cardiac arrhythmia not controlled with medical management. 3) Hypotension requiring pressor support. 4) Active Infection: Positive blood cultures for bacteria, fungus, or virus within 48 hours of T cell infusion. These delay criteria apply to subsequent doses of CART-19 cells as well.

A serum sample for potassium and uric acid will be collected before each infusion.

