#### 7.5 Efficacy

Anti-tumor activity will be assessed as a secondary trial endpoint. Anti-tumor efficacy of CART-19 cells will be determined in a follow-on study.

Another exploratory endpoint is to test the relative engraftment of CART-19 cells expressing TCR $\zeta$  or TCR $\zeta$ :4-1BB domains. It is recognized that there will be statistical power to detect only very large change in the ratio of CART-19 cells. The results of this study will provide information on the expected change in ratios of CART-19 cells from baseline to four weeks post dosing to provide guidance on which vector should be considered for a future larger study, as well as pilot data to allow determination of required samples sizes for that study.

With a total of 20 evaluable subjects in each cohort, there would be 80% power to detect a 0.76 standard deviation difference in the ratio between the two different CART-19 cell between just post dosing baseline values and values obtained from the week four apheresis, using a paired t-test at a 0.05 two-sided level of significance. With a total of seven evaluable subjects in each cohort, there would be 80% power to detect a 1.27 standard deviation difference in the CART-19 ratio under the same conditions.

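### With the 5 mixture patients planned, the exact two-sided signed-rank test named for the vector ratio cannot reach 0.05, and the plan does not fix the version of the test or the scale of the ratio

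*Combined protocol and SAP*

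**What the plan says.** Section 2 lists as a secondary objective whether the 4-1BB construct engrafts better than the TCRζ-only construct. Section 3.1 gives the design: "a cohort of 5 patients will be dosed with mixtures of" both cell types. It also states the hypothesis to be tested: "The null hypothesis is that they are equivalent".

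Section 7.7 names the analysis, and the Statistical Methodology entry of the Study Summary repeats it: "The change in the ratio of CART-19 cells over time will be compared using a Wilcoxon signed-rank test for paired data". The choice is supported by one sentence: "This nonparametric test is very efficient (>95%) compared to the t-test if the underlying data are normally distributed". Neither place gives a significance level or says whether the exact or an approximate test is meant. Neither says whether change is a difference, a fold-change or a log fold-change.

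Section 7.5 gives the power for this comparison, but "using a paired t-test at a 0.05 two-sided level of significance" and for other sample sizes: "With a total of 20 evaluable subjects in each cohort, there would be 80% power to detect a 0.76 standard deviation difference", and "With a total of seven evaluable subjects in each cohort, there would be 80% power to detect a 1.27 standard deviation difference". It concedes that only a very large change could be detected.

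Section 6.6 describes the mixture patients differently: "In subjects 15-20 who receive mixtures of CART-19 cells", which is six people if both ends are counted. Section 5.3.2 puts the comparison cohort on hold until the comparison strategy is redesigned, and requires changes to protocol and consent form, with IRB approval, before anyone in it is treated.

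**The concern.** A signed-rank test on very few pairs has a floor on its p-value set by the number of sign patterns. At 5 pairs that floor lies above 0.05. The most decisive result the cohort could produce, all five patients moving the same way, would then be reported as not significant, or as significant if the software used an uncorrected normal approximation.

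Sections 7.3 and 7.5 say the result will guide which vector goes into a larger trial. A p-value that cannot fall below 0.0625 could be read there as evidence of no difference. The caveat in 7.5 about very large changes does not cover this, because at n=5 the exact test cannot detect a change of any size.

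The scale of the ratio is a separate matter and arises at any sample size. From a baseline near 1:1, a tenfold gain is a difference of +9 and a tenfold loss a difference of -0.9. Ranking these differences treats the two directions unequally.

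**Working it through.** **Inputs.** Mixture patients: 5 (3.1); 6 if subjects 15 to 20 is inclusive (6.6); 7 or 20 evaluable (7.5). Level: two-sided 0.05 (7.5, stated for the t-test). Effect sizes: 1.27 SD and 0.76 SD (7.5). Test: Wilcoxon signed-rank, version unstated (7.7).

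**Step 1: the plan's own power figures.** For a paired t-test, df = n-1 and the noncentrality is d×√n.
- n=7, d=1.27: noncentrality 1.27×√7 = 3.36; power 79.8%. The stated 80% reproduces.
- n=20, d=0.76: noncentrality 0.76×√20 = 3.40; power 89.7%, not 80%. The difference detectable with 80% power at n=20 is 0.66 SD, so this figure does not reproduce on its stated inputs. That is a separate matter, but the paragraph has to be rewritten anyway.
- n=5, not given in the plan: d=1.27 gives noncentrality 2.84 and power of about 57%; 80% power needs 1.68 SD.

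**Step 2: floor of the exact signed-rank p-value.** Under the null all 2^n sign patterns are equally likely, so the minimum two-sided p is 2/2^n.

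| n | Minimum exact two-sided p | Exact signed-rank power at 1.27 SD, two-sided 0.05 | Paired t power at 1.27 SD |
|---|---|---|---|
| 5 | 2/32 = 0.0625 | 0% | 57% |
| 6 | 2/64 = 0.031 | 53% | 70% |
| 7 | 2/128 = 0.016 | 76% | 80% |

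Signed-rank power is from 200,000 simulated normal samples per row. At n=5 it is 0% at every effect size tried (0.76 to 3 SD), as the floor requires. If one of the five is not evaluable, n=4 and the floor is 2/16 = 0.125.

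**Step 3: dependence on the version of the test.** Take n=5 with all five changes in one direction. The statistic is 15, its null mean 7.5, and its variance 5×6×11/24 = 13.75 (SD 3.708).
- Exact: p = 0.0625.
- Normal approximation, no correction: z = 7.5/3.708 = 2.02, p = 0.043.
- Normal approximation with continuity correction: z = 7.0/3.708 = 1.89, p = 0.059.

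Only the uncorrected version crosses 0.05, and the true level of that rejection is 6.25%.

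**Step 4: the efficiency sentence.** The asymptotic relative efficiency of the signed-rank test to the t-test under normality is 3/π = 0.955, so the figure is right as a large-sample statement. At n=7 the power loss is small (76% against 80%). At n=5 and two-sided 0.05 the comparison is 0% against 57%.

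**Step 5: raw ratio or log ratio.** Illustrative data, not from the trial: seven patients, baseline ratio 1, fold-changes 7, 6, 5, 4, 3, 2 and 1/8.
- Raw differences, 4-1BB as numerator: +6, +5, +4, +3, +2, +1, -0.875. The negative value has rank 1; p = 2×2/128 = 0.031.
- Same data inverted: six negative differences between -0.857 and -0.5, and one of +7. The positive value has rank 7. Of the 128 patterns, 19 have a rank sum of 7 or less; p = 2×19/128 = 0.297.
- Log ratios: p = 0.297 in either orientation.

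**The case against.** The strongest reply is that this cohort is suspended. Section 5.3.2 requires an amendment before it opens, Section 3.1 says it waits until both constructs are settled, and all patients treated so far received only the 4-1BB product. Section 7.7 calls the analysis mainly descriptive, 7.5 calls this endpoint exploratory, and 7.3 leaves adequate power to a follow-on trial. No decision is tied to p<0.05. All of that stands and limits the weight of the point. It does not remove it: Sections 2 and 3.1 still speak of superiority and a null hypothesis, 7.7 still names an inferential test, and the stated reason for the hold is which construct to compare against, not how to analyse the result.

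A reader might infer that the efficiency sentence is false. It is not: it gives the correct asymptotic value and states its normality condition. It also links the t-test power in 7.5 to the rank test in 7.7 reasonably well at n=7. It simply gives no support at n=5.

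A reader might also infer that the comparison has zero power outright. That holds only for 5 pairs, a two-sided 0.05 level and the exact or continuity-corrected test. With six patients the floor is 0.031. Section 7.7 sets no level of its own, and at one-sided 0.05 the exact floor at n=5 is 0.031. Nothing in the plan specifies a one-sided test, but nothing in 7.7 excludes it.

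Finally, a t-test on five values rests on a normality assumption that five values cannot check, and the SDs in 7.5 refer to the ratio, not its logarithm. Both objections stand and are carried into the fix.

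**Conclusion.** The point holds in conditional form. Given 5 evaluable mixture patients (3.1) and the two-sided 0.05 level of 7.5, the exact signed-rank test has a minimum p of 0.0625 and cannot reject for any effect size. The unstated choice of version moves the same best-case result between 0.0625, 0.059 and 0.043. The plan gives no power at n=5 for either test. The numerator dependence applies if change is taken as a difference of raw ratios, which the wording allows but does not fix.

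The documents do not support saying that the trial fails an objective or that its primary conclusions are affected. This is a secondary, largely exploratory comparison in a cohort not yet open. It should be corrected before that cohort opens.

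**What to change.** Make these changes in the amendment that Section 5.3.2 already requires:

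1. In 7.7 and the Study Summary, define the endpoint as the change from post-dosing baseline to week 4 in log10(4-1BB:comparator ratio). Report the mean change with a 95% t-interval and the paired t-test. Say how a ratio is handled when one construct is undetectable.
2. Remove the efficiency sentence, or qualify it as a large-sample property that does not apply at this n.
3. If the signed-rank test is kept as support, specify the exact version and its level, and state that its minimum two-sided p at n=5 is 0.0625.
4. Reconcile the mixture cohort size across 3.1 (5), 6.6 (subjects 15 to 20) and 7.5 (7 or 20).
5. Restate the detectable difference in 7.5 for that size on the log scale. At n=5 the paired t-test has about 57% power at 1.27 SD of the analysed change, and needs 1.68 SD for 80%.

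The cost is wording only, with no extra patients or samples. The downside is reliance on approximate normality of the log ratios, which cannot be checked with 5 values; the text should say so and list the individual patient changes beside the interval.

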## **8 SAFETY AND ADVERSE EVENTS**

Safety will be assessed by monitoring and recording potential adverse effects of the treatment using the Common Toxicity Criteria version 3.0 at each study visit. Subjects will be monitored by medical histories, physical examinations, and blood studies to detect potential toxicities from the treatment.

### **8.1 Definitions**

#### **Unanticipated Problems Involving Risk to Subjects or Others**

Any incident, experience, or outcome that meets all of the following criteria:

- Unexpected in nature, severity, or frequency (i.e. not described in study-related documents such as the IRB-approved protocol or consent form, the investigators brochure, etc.)
- Related or possibly related to participation in the research (i.e. possibly related means there is a reasonable possibility that the incident, experience, or outcome may have been caused by the procedures involved in the research)
- Suggests that the research places subjects or others at greater risk of harm (including physical, psychological, economic, or social harm).

#### **Adverse Event**

An **adverse event** (AE) is any symptom, sign, illness or experience that develops or worsens in severity during the course of the study. Intercurrent illnesses or injuries should be regarded as adverse events. Abnormal results of diagnostic procedures are considered to be adverse events if the abnormality:

1. results in study withdrawal
2. is associated with a serious adverse event
3. is associated with clinical signs or symptoms
4. leads to additional treatment or to further diagnostic tests
5. is considered by the investigator to be of clinical significance

CONFIDENTIAL

### **Serious Adverse Event**

Adverse events are classified as serious or non-serious. A *serious adverse event* is any AE that is:

1. fatal
2. life-threatening
3. requires or prolongs hospital stay
4. results in persistent or significant disability or incapacity
5. a congenital anomaly or birth defect
6. an important medical event

Important medical events are those that may not be immediately life threatening, but are clearly of major clinical significance. They may jeopardize the subject, and may require intervention to prevent one of the other serious outcomes noted above. For example, drug overdose or abuse, a seizure that did not result in in-patient hospitalization, or intensive treatment of bronchospasm in an emergency department would typically be considered serious.

All adverse events that do not meet any of the criteria for serious should be regarded as *non-serious adverse events*.

### **Suspected Adverse Reaction (21 CFR 312.32(a))**

Suspected adverse reaction means any adverse event for which there is a reasonable possibility that the drug caused the adverse event. For the purposes of IND safety reporting, "reasonable possibility" means there is evidence to suggest a causal relationship between the drug and the adverse event. Suspected adverse reaction implies a lesser degree of certainty about causality than adverse reaction, which means any adverse event caused by a drug.

### **Unexpected Suspected Adverse Reaction (21 CFR 312.32(a))**

An adverse event or suspected adverse reaction is considered "unexpected" if it is not listed in the investigator brochure or is not listed at the specificity or severity that has been observed; or, if an investigator brochure is not required or available, is not consistent with the risk information described in the general investigational plan or elsewhere in the current application, as amended.

"Unexpected," as used in this definition, also refers to adverse events or suspected adverse reactions that are mentioned in the investigator brochure as occurring with a class of drugs or as anticipated from the pharmacological properties of the drug, but are not specifically mentioned as occurring with the particular drug under investigation.

### **Dose Limiting Toxicity (DLT)**

Dose limiting toxicity is defined as a grade 3 or 4 toxicity as determined by CTC 3.0, which is unmanageable, unexpected and unrelated to chemotherapy and attributable to protocol therapy. For instance, grade 4 neutropenia or thrombocytopenia related to pre-infusion chemotherapy would not be related to study drug and would not be considered as a

CONFIDENTIAL

DLT. In addition, if the toxicity is autoimmune or allergic in nature and occurs after repeat dosing, a grade 2 toxicity will be considered a DLT.

### ***Adverse Event Reporting Period***

The study period during which adverse events must be reported is normally defined as the period from the initiation of any study procedures to the end of the study treatment follow-up. For this study, adverse events are reported starting on Day 0 until the subject is off study or until year 2 end of study visit. The only exception is for patients that are discontinued due to an adverse event after enrollment and prior to infusion. This AE or SAE leading to study discontinuation will be recorded in the clinical database. Events occurring during chemotherapy, and occurring as a direct result of the cytotoxic chemotherapy will not be reported as an adverse event but should be listed under medical history.

### ***Preexisting Condition***

A preexisting condition is one that is present at the start of the study. A preexisting condition should be recorded as an adverse event if the frequency, intensity, or the character of the condition worsens during the study period.

### ***General Physical Examination Findings***

At screening, any clinically significant abnormality should be recorded as a preexisting condition. At the end of the study, any new clinically significant findings/abnormalities that meet the definition of an adverse event must also be recorded and documented as an adverse event.

### ***Post-study Adverse Event***

All unresolved adverse events should be followed by the investigator until the events are resolved, the subject is lost to follow-up, or the adverse event is otherwise explained. At the last scheduled visit, the investigator should instruct each subject to report any subsequent event(s) that the subject, or the subject's personal physician, believes might reasonably be related to participation in this study. The investigator should notify the study sponsor of any death or adverse event occurring at any time after a subject has discontinued or terminated study participation that may reasonably be related to this study. The sponsor should also be notified if the investigator should become aware of the development of cancer or of a congenital anomaly in a subsequently conceived offspring of a subject that has participated in this study.

### ***Abnormal Laboratory Values***

A clinical laboratory abnormality should be documented as an adverse event if any one of the following conditions is met:

1. The laboratory abnormality is not otherwise refuted by a repeat test to confirm the abnormality
2. The abnormality suggests a disease and/or organ toxicity
3. The abnormality is of a degree that requires active management; e.g. change of dose, discontinuation of the drug, more frequent follow-up assessments, further diagnostic investigation, etc.

CONFIDENTIAL

Medical conditions and laboratory abnormalities due to underlying disease and chemotherapy regimen are **expected** and will not be reported as adverse events (e.g. abnormal hematology values, mucositis, etc.).

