### **3.2 Primary Study Endpoints**

This phase I/IIa study is designed to test the safety and relative engraftment of the autologous T cells transduced with the anti-CD19 lentiviral vector in patients with relapsed, refractory and incurable CD19+ B cell malignancies.

Primary safety, feasibility and engraftment endpoints include:

1. Occurrence of study related adverse events, defined as NCI CTC  $\geq$  grade 3 signs/symptoms, laboratory toxicities and clinical events that are possible, likely or definitely related to study treatment at any time from the infusion until week 24. This will include infusional toxicity and any toxicity possibly related to the CART-19 cells including but not limited to:
  - a. Fevers
  - b. Capillary leak
  - c. Rash
  - d. Neutropenia, thrombocytopenia, anemia, marrow aplasia
  - e. Hepatic dysfunction
  - f. Pulmonary infiltrates or other pulmonary toxicity
  - g. Hypotension
  - h. In the allo cohort only, GVHD
2. Feasibility to manufacture CART-19 cells from patient apheresis products. The number of manufactured products that do not meet release criteria for vector transduction efficiency,

CONFIDENTIAL

T cell purity, viability, sterility and tumor contamination will be determined (defined as “manufacturing failures”).

3. Duration of *in vivo* survival of CART-19 cells is defined as “engraftment”. The primary engraftment endpoint is the # DNA vector copies per ml blood of CART-19 cells on week 4 after the first infusion. Q-PCR for CART-19 vector sequences will also be performed after each infusion, weekly x 4, monthly x 6, and every 3 months thereafter until any 2 sequential tests are negative documenting loss of CART-19 cells.
4. New onset secondary malignancies.

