#### **6.4.1 Cytoreductive chemotherapy**

It is anticipated that many patients will have been receiving chemotherapy for relapse or resistant disease. For inclusion, they will have responding or stable disease to the most recent therapy. Prior to CART-19 cell infusion and after apheresis, an additional chemotherapy cycle is planned. Patients referred with stable disease on no recent therapy will be eligible as well. The use of additional chemotherapy prior to the recommended preinfusion chemotherapy will be at the discretion of the investigator and dependent on the patient's disease burden.

When given, chemotherapy may be started approximately 8-13 days before infusion so that CART-19 cells may be given 1-5 days after completion of the chemotherapy. The timing of

CONFIDENTIAL

chemotherapy initiation therefore depends on the length of the regimen. The purpose of the chemotherapy is to induce lymphopenia in order to facilitate engraftment and homeostatic expansion of CART-19 cells. The chemotherapy may be chosen also to reduce disease tumor burden. The cytoreductive chemotherapy is not part of this investigational protocol and may be chosen and administered by the primary/referring oncologists. The choice of chemotherapy will depend on the patient's underlying disease and prior therapies. Fludarabine (30 mg/m^2/day x 4 days) and cyclophosphamide (500 mg/m^2/day x 2 days) are the agents of choice, as there is the most experience with the use of these agents in facilitating adoptive immunotherapy.

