#### **8.4.2 Stopping rules related to the CNS3 cohort**

Accrual to the CNS3 cohort will be stopped for review if:

- 1) Any subject develops a grade 5 neurological toxicity attributable to CART-19 infusion.
- 2) Any subject develops grade 3/4 neurotoxicity or agitation, confusion, delirium, or psychosis (psychiatric) toxicity that has not resolved to  $\leq$  Grade 2 within 4 weeks with or without medical intervention (ie: anti-epileptics).
- 3) Any non-resolving grade 3 or 4 neuro toxicity or death due to neuro/psychiatric toxicity clearly attributable to the CART cells will lead to a hold on any further CNS3 patients enrolled in this high risk stratum pending subsequent review.

CONFIDENTIAL

Note on attribution: Toxicity is attributable to CART-19 infusion if, in the opinion of the principal investigator or sponsor, the event was more likely than not to be caused by the CART-19 cells. In making this determination, the investigator will assess:

- Timing (most other toxicities, other than cytopenias and hypogammaglobulinemia are resolved within 28 days of infusion).
- Predisposing structural CNS lesions, prior strokes, or prior seizure history
- Neurologic baseline at study entry
- Events during CRS that may have been predisposing to CNS toxicity (such as significant coagulopathy)
- Infections are most likely attributable to cytopenias due to disease and chemotherapy, and are therefore less likely to be due to CART-19 infusion

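### A grade 3 or worse cytopenia that either chemotherapy or CART-19 could explain counts under section 3.2 but may go unreported under section 8.1, so a named primary safety event may be under-counted

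*Combined protocol and SAP*

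**What the plan says.** Section 3.2 defines the first primary endpoint as grade 3 or worse events that are "possible, likely or definitely related to study treatment at any time from the infusion until week 24". It then sets the scope: "This will include infusional toxicity and any toxicity possibly related to the CART-19 cells including but not limited to" a list whose item d is "Neutropenia, thrombocytopenia, anemia, marrow aplasia". Section 7.2.1 repeats the same grade, relatedness and time window.

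Section 8.1 governs what is recorded. Under Abnormal Laboratory Values it first says: "A clinical laboratory abnormality should be documented as an adverse event if any one of the following conditions is met", and gives three conditions. It closes by saying that conditions and laboratory abnormalities due to the underlying disease and the chemotherapy regimen are expected and "will not be reported as adverse events (e.g. abnormal hematology values, mucositis, etc". Under Adverse Event Reporting Period, an event during chemotherapy and "occurring as a direct result of the cytotoxic chemotherapy will not be reported as an adverse event" but goes to medical history. The part on hospitalization repeats the chemotherapy exclusion, there without limiting it to events during chemotherapy.

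On timing, section 6.4.1 says that when chemotherapy is given, "CART-19 cells may be given 1-5 days after completion of the chemotherapy". Section 6.6 gives the same interval. Section 7.7 plans exact 95% intervals for adverse event rates, overall and by major category. It plans no analysis of the blood counts themselves.

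**The concern.** The two sections ask different questions of the same event. Section 3.2 asks whether the cells are a possible cause. Section 8.1 asks whether disease or chemotherapy is the cause. A neutropenia that starts or persists soon after infusion, in a patient whose chemotherapy ended a few days before, can reasonably be answered yes on both. One section then counts it and the other keeps it out of the adverse event record. I found no time cut-off, comparison with pre-infusion counts or recovery rule to settle which applies.

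Attribution is made by unblinded investigators in a single-arm study, and here it decides whether the event is recorded at all, not only how it is labelled. For an event recorded as unrelated, the relatedness call can be varied in a sensitivity analysis. For an event never filed, an analysis of adverse event data has nothing to vary. The error can run in only one direction, towards a lower cytopenia rate in the primary safety endpoint.

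**Working it through.** **1. The two rules side by side, for a grade 3 or worse cytopenia after infusion**

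| Judged cause | Section 3.2 | Section 8.1 | Consistent? |
|---|---|---|---|
| Chemotherapy or disease only | Not counted | Not reported | Yes |
| CART-19 only | Counted | Reported | Yes |
| Both plausible | Counted (possibly related) | Can be withheld (due to chemotherapy or disease) | No |

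The problem lies in the third row only. How many events fall there depends on overlap in time. The 1 to 5 day interval makes overlap likely for early cytopenia when chemotherapy is given. The underlying blood malignancy is a second excluded cause, and it is present whether or not chemotherapy is given.

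**2. The plan's own figures.** Section 7.4 gives the probability of seeing no event, which is (1 − p)^n for true rate p and n subjects:

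- n = 10, p = 20%: 0.8^10 = 10.7% (plan: 11%)
- n = 10, p = 30%: 0.7^10 = 2.8% (plan: 3%)
- n = 7, p = 20%: 0.8^7 = 21.0% (plan: 21%)
- n = 7, p = 30%: 0.7^7 = 8.2% (plan: 8%)

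All four reproduce, as do the eight exact intervals in the section 7.4 table. They assume that every qualifying event is reported.

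**3. What incomplete reporting would do.** Let m be the share of product-related events put down to chemotherapy or disease and so not reported. The reported rate is p(1 − m). The documents give no value for m, so it is shown over its whole range. They give no cytopenia rate either, so p is borrowed from section 7.4, where it stands for toxicity in general. The last column is 72 × p(1 − m), with 72 the planned number infused.

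| p | m (assumed) | p(1 − m) | P(none reported), n = 7 | P(none reported), n = 10 | Expected reported in 72 |
|---|---|---|---|---|---|
| 20% | 0 | 20% | 21.0% | 10.7% | 14.4 |
| 20% | 0.5 | 10% | 47.8% | 34.9% | 7.2 |
| 20% | 0.9 | 2% | 86.8% | 81.7% | 1.4 |
| 20% | 1 | 0% | 100% | 100% | 0 |
| 30% | 0 | 30% | 8.2% | 2.8% | 21.6 |
| 30% | 0.5 | 15% | 32.1% | 19.7% | 10.8 |
| 30% | 0.9 | 3% | 80.8% | 73.7% | 2.2 |
| 30% | 1 | 0% | 100% | 100% | 0 |

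**4. The planned interval does not show the loss.** Exact 95% (Clopper-Pearson) intervals:

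- 14/72 = 19.4%: 11.1% to 30.5%. If half are reported, 7/72 = 9.7%: 4.0% to 19.0%.
- 22/72 = 30.6%: 20.2% to 42.5%. If half are reported, 11/72 = 15.3%: 7.9% to 25.7%.

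In both pairs the interval from the halved count lies below the full observed rate. An exact interval covers sampling error and does not reflect events missing from the record.

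**The case against.** The strongest reply is that section 8.1 excludes by cause. It withholds only what is due to disease or chemotherapy, so a cytopenia attributed to CART-19 stays reportable under section 3.2 and under the three laboratory conditions. The definition of dose-limiting toxicity draws the same line. This stands. A reader might infer that the plan removes product-related cytopenia before analysis; the text does not prescribe that. It leaves room for misattribution.

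Other points also limit the size of the problem:

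- The Preexisting Condition paragraph requires an adverse event if the frequency, intensity or character of a condition worsens. That gives a route for a cytopenia that deepens after infusion. It does not clearly cover one that only lasts longer.
- Chemotherapy is conditional (6.4.1, 7.1), and later infusions may fall at day 14 or after, so the 1 to 5 day overlap does not apply to every patient or every infusion.
- Cytopenia that appears after counts have recovered is harder to put down to chemotherapy.
- Section 15.1 schedules a blood count at almost every visit to year 2. The information is not lost; no analysis of it is planned.
- It is tempting to read section 8.4.2 ("most other toxicities, other than cytopenias and hypogammaglobulinemia are resolved within 28 days of infusion") as an admission that the cells cause prolonged cytopenia. That note concerns attribution of neurological toxicity in the CNS3 cohort and does not assign cytopenia to the product. Its last item speaks of cytopenias from disease and chemotherapy.

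It can also be said that the endpoint rests on attribution by design, in a study that is mainly descriptive. That is true, but it does not say what to do when both causes are possible.

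**Conclusion.** Sections 3.2 and 8.1 conflict for a cytopenia that both chemotherapy or disease and the cells could explain, and no rule settles it. A named component of the primary safety endpoint may be under-counted, and the analysis in section 7.7, which uses adverse event rates alone, cannot correct it. The direction is downward. The size cannot be estimated from the documents: it runs from nothing to all of the dual-cause events.

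The numerical illustration rests on two assumptions, a true rate of 20% or 30% and a chosen share misattributed. A reader might go further and picture 14 to 22 of 72 patients recorded as none, with a 0/72 interval of 0% to 5.0%. That needs every such event to be misattributed, at a rate the documents do not give. It is an extreme case and should not be cited as the expected effect.

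This should be corrected because the component is named in the primary endpoint and the correction is cheap. It does not undermine the rest of the safety plan.

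**What to change.** 1. **Section 8.1, reconciled with section 3.2.** State that the non-reporting rule (under Abnormal Laboratory Values, Adverse Event Reporting Period and the part on hospitalization) does not apply to (a) any grade 3 or worse cytopenia after infusion judged at least possibly related to CART-19, whether or not chemotherapy or disease is also a possible cause, or (b) any grade 3 or worse cytopenia present at or after Day 28. Part (a) settles early dual-cause events; part (b) covers prolonged ones without relying on attribution.
2. **Section 7.7.** Tabulate grade 3 or worse neutropenia, thrombocytopenia and anaemia from the scheduled blood counts at Day 28 and monthly to month 6, regardless of attribution, beside the attributed adverse event rate. Show the pre-infusion counts. Censor, or show separately, counts after relapse, new antineoplastic therapy or stem cell transplant, which would otherwise be mixed in. Marrow aplasia cannot be read from blood counts and stays with the adverse event record.

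The cost is a short addition to section 8.1 and one table. No new visit or sample is needed. The documents do not say whether count values are entered on the case report form; if they are not, these time points need data entry. The downside is that some cytopenia due to chemotherapy or disease will be included, and the reported rate may look less favourable. The Day 28 start and the pre-infusion counts limit this for the table.
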